#### 10.1.2 Determination of Sample Size

The sample size for Part 1 of this study was determined by clinical rather than statistical considerations. Approximately 20 patients will be treated in Part 1 of this study (Dose Escalation) to establish dose limiting toxicities (DLT), maximum tolerated dose (MTD), and the recommended Phase 2 dose (RP2D).

After the completion of Part 1 of this study, up to 40 additional AML or MDS patients with or without RAS mutations will be treated with the RP2D of BVD-523. The purpose of the second phase of this study is to document that there is some evidence of a response. With 20 subjects in each group, there is an 88% probability of seeing at least one positive response in each group if the true response rate is at least 10%.

The observation of DLTs in more than 33% of patients in any Part 2 cohort with at least 6 patients enrolled at any time during Part 2 will trigger temporary stopping of patient enrollment and revision of the definition of the MTD and RP2D in the specific cohort. Subsequent patients will be treated with a dose lower than the initial RP2D and this dose will be determined in discussion with the Clinical Investigators, the Medical Monitor, and the Sponsor.

Up to 6 study centers are expected to enroll patients for this study.

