#### **Statistical Methods**:

The sample size for Part 1 of this study was determined by clinical rather than statistical considerations. Approximately 20 patients will be treated in Part 1 of this study (Dose Escalation Phase) to establish dose limiting toxicities (DLT), maximum tolerated dose (MTD), and the recommended Phase 2 dose (RP2D).

After completion of Part 1 of this study, Part 2 will commence. In Part 2, up to 40 additional AML or MDS patients will be recruited to one of two groups- Group 1: patients with positive RAS mutant AML or MDS and Group 2: patients with negative RAS mutant AML or MDS will be treated with the RP2D of BVD-523. The purpose of the second phase of this study is to document evidence of response. With 20 subjects in each group, there is an 88% probability of seeing at least one positive response in each group if the true response rate is at least 10%.

The observation of DLTs in more than 33% of patients in either Part 2 cohort with at least 6 patients enrolled at any time during Part 2 will trigger temporary stopping of patient enrollment and revision of the definition of the MTD and RP2D in the specific cohort. Subsequent patients will be treated with a dose lower than the initial RP2D and this dose will be determined in discussion with the Clinical Investigators, the Medical Monitor, and the Sponsor.

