# 4 SELECTION OF PATIENTS

## 4.1 NUMBER OF PATIENTS

In this study, up to approximately 20 patients with AML or MDS, regardless of RAS mutation status, will be enrolled in Dose-escalation Part 1. Three to six patients per treatment cohort will be assigned to receive sequentially higher oral doses of BVD-523.

In the Cohort-expansion Part 2, additional patients with RAS mutant positive AML or MDS and RAS mutant negative AML or MDS will be recruited for treatment at the RP2D determined from Part 1 above.

Part 2 patients will receive twice daily oral doses of BVD-523 in 21-day treatment cycles until disease progression, unacceptable toxicity, or another withdrawal criterion is met. Treatment cycles will occur consecutively without interruption except when necessary to manage AEs.

Total enrollment for Part 2 is targeted for up to approximately 40 patients. Patients will be enrolled into 1 of 2 treatment groups. Group assignments are made according to the following disease characteristics:

- Group 1: Patients with RAS mutant positive AML or MDS; n (evaluable)  $\leq 20$
- Group 2: Patients with RAS mutant negative AML or MDS; n (evaluable)  $\leq 20$ .

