### 2.2 TREATMENT GROUPS

This Phase 1/2 study is single-arm.

In Phase 1 (Dose Escalation) the treatment group is subjects treated with orally administered BVD-523 BID.

In Phase 2 (Cohort Expansion) the treatment group is subjects treated with orally administered BVD-523 BID at the RP2D in one of two groups: RAS mutant positive or RAS mutant negative.

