### 6.2 STRATA AND COVARIATES

No covariates will be accounted for in Part 1. In Part 2, analyses will be conducted separately by RAS mutation status (positive or negative).

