## 14.2 EFFICACY SUMMARY FIGURES AND TABLES

Table	Title	Population
Part II - Table 14.2.1.1.1	AML Disease Response by Bone Biopsy (IWG 2003)	mITT Population
Part II - Table 14.2.1.1.2	AML Disease Response by Bone Biopsy (IWG 2003)	PP Population
Part II - Table 14.2.1.2.1	MDS Disease Response by Bone Biopsy (IWG 2006)	mITT Population
Part II - Table 14.2.1.2.2	MDS Disease Response by Bone Biopsy (IWG 2006)	PP Population
Figure	Title	Population

N/A

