### 16.2.6 Individual Efficacy Response Data

- Part II Listing 16.2.6.1 AML Disease Response per IWG 2003
- Part II Listing 16.2.6.2 MDS Disease Response per IWG 2006

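### Does the 88% chance of a response in each RAS group overstate what Part 2 can show, and does the SAP need another response table?

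*Protocol*

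**What the plan says.** Protocol 10.1.2 and the Statistical Methods part of the Synopsis both describe Part 2 as seeking some evidence of response, and both attach one probability to its size: "With 20 subjects in each group, there is an 88% probability of seeing at least one positive response in each group", conditional on a true rate of 10% or more. Protocol 4.1 makes 20 a ceiling on the evaluable patients in each RAS group. SAP 4 keeps 20 per group but omits the 88% and refers instead to the size of similar Phase 1 oncology trials.

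SAP 2.2 has Part 2 patients treated "at the RP2D in one of two groups: RAS mutant positive or RAS mutant negative", so the RAS groups are the Part 2 treatment groups. SAP 6.2 requires Part 2 analyses to be done separately by RAS status, and SAP 6.6 sorts Part 2 listings by it as well. SAP 5.3 and 5.4 assign the mITT and PP populations to Part 2 response.

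The four efficacy tables in SAP 14.2 are titled by disease and criteria: AML under IWG 2003 and MDS under IWG 2006, each for mITT and PP. The two response listings follow the same pattern, for example "AML Disease Response per IWG 2003". SAP 9.3 plans no further efficacy analysis. Protocol 10.3.6 and SAP 9.2 say that no formal efficacy analysis will be done.

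**The concern.** Three things look wrong at first.

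- **The probability.** The phrase about each group can mean any given group, or both groups at once. The second event is less likely. A reader who takes 88% as the chance that both groups respond would put the risk of an empty group at 12%, when it is nearer 23%.
- **The display.** The 88% refers to responders out of 20 in a RAS group, AML and MDS together. No listed title is for that count, and the disease-specific titles suggest a different split.
- **The interval and the definition.** No interval for response is stated, although SAP 11 gives 95% intervals for t1/2 and tmax. A small count without an interval is easily over-read. Neither the sample-size text nor SAP 9.2.2 says which IWG categories make a positive response.

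What would be at stake is the reading of the Part 2 response results: a group with no responders might be taken as evidence of inactivity, or the design might be thought stronger than it is.

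**Working it through.** **Inputs.** n = 20 per group and true rate p = 0.10, the low end of the stated range (Protocol 10.1.2 and Synopsis). The groups are different patients, so independence is assumed.

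**The plan's own figure.** For one group, P(at least one response) = 1 − (1 − p)^n = 1 − 0.9^20 = 1 − 0.1216 = 0.8784. This reproduces the 88%.

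**Other readings of the same words, at p = 0.10 in both groups.**

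| Event | Formula | Result |
|---|---|---|
| Both groups show at least one | 0.8784² | 77.2% |
| Exactly one group does | 2 × 0.8784 × 0.1216 | 21.4% |
| Neither does | 0.1216² | 1.5% |
| At least one response among all 40 | 1 − 0.9^40 | 98.5% |

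The chance that at least one group is empty is 1 − 0.7716 = 22.8%. Neither the both-groups reading nor the all-40 reading gives 88%, so the figure itself shows which event was calculated.

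**Size of the gap.** The text says at least 10%, so 87.8% and 77.2% are both lower bounds over the stated range. Setting (1 − (1 − p)^20)² = 0.88 gives p of about 0.130, so the both-groups statement would be true at a rate of 13%. At p = 0.10 it would take 27 per group: (1 − 0.9^27)² = 0.887. That number only scales the gap; it is not a proposal.

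**Fewer evaluable patients.** Because 20 is a ceiling, two illustrative assumptions: with 18 per group, 85.0% for one group and 72.2% for both; with 15 per group, 79.4% and 63.1%.

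**Intervals.** Exact (Clopper-Pearson) 95% limits at n = 20:

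- 0/20: 0 to 16.8%, where the upper limit is 1 − 0.025^(1/20)
- 1/20: 0.1% to 24.9%
- 2/20: 1.2% to 31.7%

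So 0/20 does not exclude the 10% planning rate. Each interval needs only the count and the denominator.

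**Displays.** No table or figure title in SAP 14.1 to 14.4 names the RAS groups. That includes demographics, which SAP 8.2 requires by treatment group. A title without RAS therefore says little about the columns beneath it. The shells are in a separate attachment that is not available here. With SAP 6.2 in force, RAS columns in the AML and MDS tables are the natural expectation. If they are there, the pooled count per RAS group is one addition across two tables. It can in any case be counted from the two response listings, which SAP 6.6 orders by RAS status.

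**The case for a change.** The best case for a change is that this is the only probability offered for the size of Part 2, and that response is not peripheral: Protocol 10.3.5 lists it under primary endpoints and SAP 9.1 names it for Part 2. The wording does admit two events, and nothing in the sentence picks one. The quantity behind the 88% has no display titled for it. Whether marrow CR or hematological improvement counts as a response in MDS would change the numerator, and that is not written down. The remedy would be cheap: a phrase, a line and a descriptive table.

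Part of this stands. A phrase such as 'in a given group' would be clearer. The visible text gives no interval for response and no named responder set.

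The rest is weaker. The sentence first speaks of 20 subjects in each group, which is plainly per group, and the natural reading carries that through to the probability. The stated aim is some evidence of response, and it does not require a response in both RAS groups, so 77% describes an event that the protocol does not set as a goal. The display complaint rests on titles alone. A pooled AML and MDS table would mix two sets of response criteria, and SAP 9.2.2 deliberately assesses the diseases differently. The response data are recorded by IWG category, with everything else collected as less than PR. If the tables report those categories, as their titles suggest, a reader can form any responder set from them.

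**Conclusion.** No change follows. The 88% is correct for one given RAS group of 20 at a true rate of 10%, and that is the only reading tried that reproduces it. The both-groups figure of 77.2% rests on independent groups and exactly 10% in each, and it rises with the true rate. The sentence is loosely worded, but the sample size, the analyses and the decisions do not depend on it.

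The reporting points are gaps that analysts can fill sensibly. SAP 6.2 already calls for the split by RAS status, an exact interval can be computed from any reported count and denominator, and category counts by disease give a sound descriptive account in a plan that makes no formal efficacy claim. Whether the tables already carry RAS columns cannot be judged without the shells, so that part is held with less confidence than the arithmetic. An exact interval and a named responder set would help a reader of the report, but the plan as written would reach the same conclusion without them.

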Part	2: BVD-523, recommended Phase	2 dose (RP2D), taken orally with	at least 8 ounces of water twice-daily		

Sponsor:	Investigational Product:	Developmental Phase:
BioMed Valley Discoveries, Inc.	BVD-523	Phase 1/2

for each 21 day cycle. Dosing of each subject may continue until the subject is discontinued from the study. A subject that has a Dose Limiting Toxicity (DLT) may be dose reduced or be withdrawn from the study depending upon the decision of the Safety Monitoring Committee (which includes the Sponsor, Medical Monitor and the study investigator).

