#### Part 1 Dose-escalation Phase:

A classic "3+3" design will be used to establish dose limiting toxicities (DLT), maximum tolerated dose (MTD), and the recommended Phase 2 dose (RP2D). Three to six patients per treatment cohort will be assigned to receive sequentially higher oral doses of BVD-523 on a twice daily schedule (b.i.d.) for 21 days (a "Cycle"), starting at a dose of 300 mg twice daily. Patients will receive twice-daily oral doses of BVD-523 until disease progression, unacceptable toxicity, or a clinical observation satisfying another withdrawal criterion is noted. Treatment cycles will occur consecutively without interruption, except when necessary to manage adverse events. All dose-escalation decisions will be based on Cycle 1 safety data and doses will not be escalated unless the patients receiving the highest current dose have been observed for at least 21 days (1 cycle).

The classic 3 + 3 design will be conducted as follows. Initially, 3 patients will be enrolled to a cohort; the occurrence of a single drug-related DLT in one of these 3 patients will prompt enrollment of up to 3 additional patients to that same cohort. When more than 1 DLT occurs in

 $\leq$  6 patients in a dosing cohort, dose escalation will be stopped and this dose level will be identified as the non-tolerated dose.

Doses between the non-tolerated dose and the preceding lower dose, where  $\leq 1$  DLT occurred, may be explored to more precisely define the MTD. This strategy allows for a rigorous determination of MTD, especially if the dose increase that resulted in determination of the non-tolerated dose is relatively large (i.e., > 50%).

During the study, the Safety Monitoring Committee may request that cohorts be enlarged or that evaluation of intermediate doses between 2 planned escalation steps be explored. Such requests will be discussed with the Investigator(s), Sponsor and Medical Monitor, and should be based on all data existing at that time, including safety and clinical activity, determinations of pharmacokinetics, pharmacodynamics, and cumulative toxicity. Before each escalation, investigators will be consulted to ensure that all involved agree with the escalation decision.

In addition, intra-patient dose escalation will be allowed after a patient has completed at least one cycle at their assigned dose, with escalation up to a dose where at least 3 patients have completed at least one cycle.

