### 3.1.4 Definition of MTD, DLT, and RP2D

#### 3.1.4.1 Definition of Maximum Tolerated Dose (MTD)

MTD is defined as the highest dose cohort at which < 33% of patients experience BVD-523 related DLTs in the first 21 days of treatment.

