## 5.2.2 Visit 2 (Day 1 ± 0); Baseline/Drug Dispensing/Initiation of Treatment

The following procedures will be performed at Visit 2 (Baseline):

- Review Screening/Enrollment Form to confirm consent to enroll obtained from Medical Monitor or Sponsor.
- Review all inclusion and exclusion criteria to ensure that patients meet all inclusion criteria and none of the exclusion criteria.
- Review medical history for any changes since Screening Visit.

- Record medications including start/stop dates, indication, dose and frequency for any changes since Screening Visit.
- Perform and record physical examination.
- Measure and record weight in kg.
- Assess and record performance status (ECOG) if not done during Screening Visit within 72 hours of start of treatment.
- Record vital signs (body temperature, systolic / diastolic BP and pulse rate).
- ONLY if the screening pregnancy test was performed more than 1 day previously, collect blood for a repeat serum pregnancy test for female patients who are not postmenopausal or surgically sterile.
- Collect pre-dose blood samples for pharmacokinetic (PK), pharmacodynamic (PD), and PBMC analyses.
- Collect pre-dose blood samples for blood chemistries, hematology and creatinine clearance if not done during Screening Visit within 72 hours of start of treatment.
- Collect pre-dose urine samples for urinalysis.
- Administer first dose of BVD-523.
- Collect post-dose blood samples for pharmacokinetic (PK), pharmacodynamic (PD), and PBMC analyses.
- Assess and record adverse events (AEs).
- Dispense study drug and instruct patients how to take study drug, daily every 12 hours ± 2 hours with at least 8 ounces of water on an empty stomach, i.e., fasting (30-60 minutes before food or 2 hours after food).
- Inform patients of the potential photosensitizing effects of BVD-523 and instruct them to avoid sunlight and wear protective clothes, sunglasses, and apply sunblock when outside, including when driving a car.

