# 8 TREATMENT

The safety and PK of BVD-523 will be tested in sequentially increasing doses starting at 300 mg twice daily, initially in patient cohorts of 3 patients (for tabular summary, see Table 3.2). Dose escalations of BVD-523 will occur in 100% increments in cohorts until one patient experiences a study related  $\geq$  Grade 2 toxicity (excluding alopecia or diarrhea), after which dose increases will be  $\leq$  50%. If one patient in a 3 patient cohort experiences a DLT as defined in Table 3.2, up to 3 additional patients will be treated at this dose level. If more than one DLT occurs in  $\leq$  6 patients, this dose level will be defined as the non-tolerated dose and dose escalation will be stopped.

Doses will not be escalated unless the patient(s) receiving the highest current dose have been observed for at least 3 weeks and dose-limiting side effects have been reported in less than 2 of 6 patients assigned to a given dose. Before each escalation, Clinical Investigators will be consulted to ensure that all involved agree with the escalation decision. Once the RP2D has been identified, up to 40 additional patients with pre-defined genetic types will be treated at this dose in Part 2.

Patients experiencing DLT or unacceptable toxicity will have their treatment interrupted until the toxicity returns to  $\leq$  Grade 1 or pre-treatment baseline (whichever is more severe). Resumption of BVD-523 treatment may then be at the next lower dose level where the safety profile has previously been established or between the dose level yielding unacceptable toxicity and the previous dose level, aligning with capsule dose availability.

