#### **AE Coding**

Any AE including SAE in verbatim term will be coded in accordance with the Medical Dictionary for Regulatory Activities (MedDRA®) dictionary version 17.1 to a system organ class (SOC) and preferred term (PT) within each SOC. Analysis of AEs will then be performed using SOCs and PTs.

Dose Limiting Toxicities, Maximum Tolerated Dose, and Recommended Phase 2 Dose

As specified in Section 3.1, a DLT is defined as a **BVD-523 related toxicity** in the first 21 days of treatment that results in:

- Any treatment-emergent study drug related Grade 3 or Grade 4 non-hematologic toxicity unless clearly and incontrovertibly unrelated to BVD-523. Exceptions are Grade 3 or 4 nausea or vomiting that is controllable by anti-emetics or Grade 3 or 4 diarrhea controllable by optimal therapy such as loperamide. Grade 3 laboratory investigations other than serum creatinine, bilirubin, AST or ALT will not be considered a DLT unless they are associated with clinical manifestations.
- Study-drug related Grade 4 thrombocytopenia that was not present at study entry and that does not resolve within 7 days, unless clearly and incontrovertibly unrelated to BVD-523.
- Febrile neutropenia or Grade 4 neutropenia that was not present at study entry and that does not resolve within 7 days, unless clearly and incontrovertibly unrelated to BVD-523.
- Prolonged myelosuppression or pancytopenia with a hypocellular bone marrow and no marrow blasts lasting for 6 weeks that is not related to disease progression.
- Any study drug related toxicity that results in treatment delays of > 4 days, except when subject is experiencing rash in which case, subject may be off drug for up to 7 days while receiving treatment.

As specified in Section 3.1, the MTD is defined as the highest dose level at which no more than 1 of 6 subjects experiences BVD-523 related DLTs in the first 21 days of treatment. The RP2D may be as high as the MTD and will be determined in discussion with the Clinical Investigators, the Medical Monitor, and the Sponsor. Observations related to pharmacokinetics (PK), pharmacodynamics (PD), and any cumulative toxicity observed after multiple cycles may be included in the rationale supporting the RP2D.

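### The Part 2 DLT trigger waits for the sixth patient in a cohort even when two earlier DLTs have already settled its outcome; pausing at the second DLT is a cheap improvement of modest size

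*Protocol*

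**What the plan says.** The Part 2 trigger appears twice. Protocol section 10.1.2 sets it at "DLTs in more than 33% of patients in any Part 2 cohort with at least 6 patients enrolled at any time during Part 2". The synopsis, under Statistical Methods, has the same rule for DLTs "in either Part 2 cohort with at least 6 patients enrolled". When it fires, enrolment in that cohort stops temporarily, the MTD and RP2D are revised for it, and later patients get a lower dose. Each cohort has up to 20 patients.

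Three other places show how the plan treats two DLTs in six:

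- Protocol 3.1.4.1 defines the MTD as the "highest dose cohort at which < 33% of patients experience" a drug-related DLT in the first 21 days.
- SAP 10.2 says that "the MTD is defined as the highest dose level at which no more than 1 of 6 subjects experiences BVD-523 related DLTs" in that period.
- Protocol section 8 (Part 1): with more than one DLT in six or fewer patients, "this dose level will be defined as the non-tolerated dose and dose escalation will be stopped".

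Other controls also reach Part 2. In the synopsis, a patient with a DLT "may be dose reduced or be withdrawn from the study depending upon the decision of the Safety Monitoring Committee". Section 3.1.3 provides for periodic committee review, which may affect the RP2D. Sections 3.2 and 7.1 provide for committee review of SAEs, with automatic suspension for a related death or anaphylaxis. Section 5.2.2, applied to Part 2 by section 5.5, has the site "confirm consent to enroll obtained from Medical Monitor or Sponsor" before the first dose. None of these states a number of DLTs.

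**The concern.** The trigger is the only numeric DLT rule for Part 2, and a minimum of six enrolled patients is built into it. If its outcome can be fixed before the sixth patient enrols, the text allows further patients to start the same dose after the decision to pause is no longer open. This matters most if the RP2D proves too toxic in one RAS group. A single 3+3 cohort gives limited assurance against that, because a dose with a true 40% DLT rate passes one such cohort about 31% of the time (shown in the working).

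**Working it through.** **1. The plan's own figure.** The only probability stated for Part 2 is 88% for at least one response in 20 patients at a 10% rate: 1 − 0.9^20 = 0.878 per group, which reproduces. The plan gives no operating characteristic for the DLT trigger.

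**2. The boundary.** The smallest DLT count above 33% is 2 at n = 6 (33.3%), 3 at n = 7 to 9 and 4 at n = 10 to 12, rising to 7 at n = 19 and 20. Counting 2 of 6 as too many agrees with the MTD definition, the SAP and the Part 1 rule.

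**3. Certainty.** When the sixth patient enrols, at most six patients are in the denominator. Two DLTs seen by then give at least 2/6, which exceeds 33% whatever happens to the others. This needs patients to enrol one at a time, since going from five to seven at once gives 2/7 = 28.6% and no trigger.

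**4. Patients spared if each outcome is known before the next enrolment.** The second DLT falls on patient k with probability (k − 1)p²(1 − p)^(k−2), and 6 − k patients then need not start. The expected number spared is the sum over k = 2 to 5 of (k − 1)p²(1 − p)^(k−2)(6 − k).

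- p = 0.40: 0.640 + 0.576 + 0.346 + 0.138 = 1.70
- p = 0.20: 0.160 + 0.192 + 0.154 + 0.082 = 0.59
- p = 1/6: 0.111 + 0.139 + 0.116 + 0.064 = 0.43

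The chance of a second DLT by patient 5 is 66%, 26% and 20% respectively.

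**5. Staggered accrual.** The synopsis gives 18 to 24 months for Part 2. Twenty patients per cohort in that time is one every 27 to 36 days, or about one a month. Simulation assumptions: random accrual, DLT onset uniform over 21 days, denominator of all enrolled, rule checked at each enrolment and each DLT.

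| Assumed DLT rate | Pause probability at 1/month, with or without the change | Mean patients at initial RP2D, 1/month | Same, 4/month | Same, outcomes known in sequence |
|---|---|---|---|---|
| 1/6 | 30.4% | 16.0 to 15.7 | 16.9 to 16.7 | 15.8 to 15.4 |
| 20% | 41.1% | 14.7 to 14.2 | 15.7 to 15.4 | 14.4 to 13.8 |
| 30% | 71.4% | 11.0 to 10.0 | 12.1 to 11.5 | 10.6 to 9.5 |
| 40% | 91.2% | 8.2 to 6.8 | 9.2 to 8.3 | 8.0 to 6.3 |

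Each cell of means runs from the current rule to the rule with the added sentence. The two rules disagreed on whether to pause in 0 of 640,000 simulated cohorts (16 settings of 40,000).

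**6. Late confirmation.** Some DLTs in section 3.1.4.2 are confirmed only after days, such as cytopenias unresolved at 7 days or treatment delays over 4 days. A 7-day lag on every DLT, as an upper case, reduces the 40% saving to about 1.3 at one patient a month and 0.6 at four. At a rate of 1/6 and four a month it is about 0.14.

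**7. If 33% means strictly more than one third.** Then 3 of 6 are needed, and two early DLTs settle nothing. With outcomes known in sequence, pausing at the second DLT would raise the pause probability from 17.5% to 25.6% at 1/6 and from 27.2% to 35.7% at 20%. With staggered accrual the increase is about 6 to 8 percentage points.

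**8. Why 40% is worth considering.** One 3+3 cohort is passed with probability (1 − p)³ + 3p(1 − p)^5. At p = 0.40 this is 0.216 + 0.093 = 0.309; at 30% it is 49% and at 50% it is 17%.

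**The case against.** Six is a defensible minimum. The trigger also forces a dose reduction, and six patients inform the choice of the lower dose better than two to five. Oversight does not wait for six: the committee decides on each patient with a DLT, drug-related SAEs are reviewed at once, and every enrolment needs consent. The 40% rate is a stress case. The SAP (section 5.2) gives the RP2D as 600 mg, which was also the MTD in the 27-patient solid-tumour study, where one of the five patients with DLTs was at that dose. At tolerable rates the saving is a fraction of a patient.

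Most of this stands and limits the size of the point. It does not remove it: none of those controls sets a DLT count or obliges anyone to stop, and a patient enrolled after the second DLT may inform the next dose but cannot affect the decision to pause.

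Two stronger readings are tempting, and the documents do not support them. A reader might infer that Part 2 has no safety control below six patients; the controls above show otherwise. A reader might also infer that Part 2 drops a protection that Part 1 gives between patients. The Part 1 rule governs escalation: "doses will not be escalated unless the patients receiving the highest current dose have been observed for at least 21 days". That wait lies between dose levels, and Part 1 states no stagger between patients within a cohort. Part 1 therefore supports the reading of 2 of 6 as too many, but it is not a like-for-like precedent for stopping enrolment at a single dose.

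**Conclusion.** The point holds as a cheap improvement of modest size. On the literal threshold, two DLTs among two to five enrolled patients fix the pause at the sixth, yet the text lets enrolment continue until then. At an assumed 40% DLT rate, stopping at the second DLT spares about 0.6 to 1.7 patients per cohort: about 1.4 to 1.5 at one patient a month, about 1.0 at four a month, and about 0.6 at four a month with a 7-day confirmation lag. At 1/6 to 20% it spares about 0.1 to 0.6.

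The result that no pauses are added rests on three conditions: 33% is literal, the cohort would reach six (the groups have a cap of 20 but no minimum), and patients enrol one at a time. The DLT rates, accrual pattern and onset times are assumptions. Nothing here disputes the per-cohort rule, the 33% level or the 88% figure.

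**What to change.** Keep the per-cohort rule. In Protocol section 10.1.2 and in the synopsis, add: *Enrolment in a cohort is also paused as soon as a second DLT occurs while fewer than six patients are enrolled in it.* In the same places, state that 2 of 6 counts as more than 33%. What follows a pause stays as written, using follow-up of patients already dosed.

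The cost is one added sentence and one clarification in two places, with no extra patients or visits. The real downside is that the lower dose is then chosen with two to five rather than six patients enrolled. If the sponsor meant strictly more than one third, the sentence should name the third DLT below six instead. At 40%, with outcomes known in sequence, that version takes the mean from 9.6 to 9.0 patients at the initial RP2D.

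A wider rule, pausing at a second DLT among the first six treated even after a seventh has enrolled, is a trade-off and not part of this fix. At a rate of 1/6 it raises pauses from 30.4% to 31.6% at one patient a month and from 24.7% to 29.8% at four a month.
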